## Research Procedures

Check all boxes that apply to the research:

Audio, Video, Digital or Image Recording and/or Photography for Collection of Research Data

Clinical Investigation involving an Investigational Device

Other Non-invasive Physical Measurements (e.g., ECG, EEG, moderate exercise, muscular strength testing, body composition assessment)

Will **deception or incomplete disclosure** be involved in the research?

No

## Study Design

Include an explanation of the study design (e.g., randomized placebo-controlled, cross-over, cross-sectional, longitudinal, etc.) and, if appropriate, describe stratification/randomization/blinding scheme:

Aim 1 is a parallel, 2-arm randomized controlled Phase 2 clinical trial. Aim 3 is a randomized, 2-arm randomized controlled study (not a clinical trial). They will produce the following study groups 1. Aim 1 – randomization 1:1 between 2 groups as follows: a. Group 1 (40 subjects): undergoing multiple sessions of 1 hour BCI-FES therapy followed by 1 hour of conventional physical therapy b. Group 2(40 subjects): undergoing multiple sessions of 2 hour conventional physical therapy sessions 2. Aim 3 – randomization 1:1 between 2 groups as follows: a. Group 3 (10 subjects): BCI-FES therapy (no conventional physical therapy) b. Group 4 (10 subjects): BCI-robotic orthosis therapy (no conventional physical therapy) BCI-FES therapy: Group 1 subjects will undergo placement of a 4-channel EEG cap using standard technique (Cz, Cpz, C1, C2) and be connected to our custom BCI system (from Study 1a). Note that based on Study 3, this electrode selection will likely capture brain areas subserving dorsiflexion for all stroke subjects. Subjects will provide 5 min of training EEG data as they engage in alternating epochs of idling and attempted foot dorsiflexion (of the paretic side). The automated software will analyze the data to generate and calibrate a BCI decoder (additional 5-10 mins). In the online phase (involves actively operating the BCI system in real-time), the subjects will perform 20-25 BCI-FES runs (total of 1 hour). In each run, subjects will follow 10 alternating epochs of 10-s long idling/dorsiflexion textual cues, and respond by either idling or attempting dorsiflexion to elicit BCI-FES mediated contractions of the TA muscle. A total of 12 sessions will be performed at a rate of 3x/week (over 4 weeks). Each BCI-FES therapy session will be followed by 1 hour of conventional physiotherapy as described below. Conventional Physical Therapy: This will consist of a standardized regimen of activities typical of conventional post-stroke gait therapy, including passive/active range of motion exercises (to reduce/prevent excessive plantarflexor contractures), lower-extremity muscle strengthening, and a progression from treadmill to overground walking exercises. A total of 12 sessions will be performed at 3x/week. For Group 1, conventional physiotherapy will immediately follow each BCI-FES session and last for 1 hour. In the dose-matched control group (Group 2), it will be 2 hours/session. Subjects will not be allowed to undergo outside physiotherapy for the entire

study. A commercial company will be used to assign patients a 30 minute home exercise program to be completed 4 times a week with compliance assessed via non-invasive sensors. For those without a mobile device, a pen and paper version of the home exercise program will also be available. Aim 3: The aim is designed as a randomized controlled study with two arms: BCI-FES dorsiflexion therapy and BCI-robotic orthosis therapy. A total of 20 subjects will be recruited and randomized with 1:1 ratio into the two arms. The primary outcome is gait velocity, and the secondary outcomes are ankle torque and active range of motion. The main interest is to evaluate if the correlation between  $M1 \rightarrow EMG$ ,  $w$ , (normalized range: 0-1), and gait velocity is different between the two study groups averaged over time after treatment, adjusted for baseline outcome measure. For example, with outcome gait velocity, the analysis will be based on a regression model with group,  $w$ , and their interaction, adjusted for baseline gait velocity. The relationship between both  $w$  with secondary outcomes will be similarly analyzed. TR-NIRS parameters will be measured at the TA muscle of stroke patients while they attempt dorsiflexion while seated with the tibia perpendicular to the ground.

Measurements pertaining to oxygen metabolism at the TA muscle will be acquired by placing the source and detector fibers on the skin surface positioned over the muscle (using the adhesive pads). This setup allows for the collection of metabolic data in real time while either the BCI-FES or BCI-robotic orthosis systems are being used.

Provide precise definitions of the study endpoints and criteria for evaluation; if the primary outcomes are derived from several measurements (i.e., composite variables) or if endpoints are based composite variables, then describe precisely how the composite variables are derived:

Aim 1: The primary outcome measure will be gait velocity, which is directly linked to disability and social re-integration after stroke. Gait velocity will be assessed by measuring the time to traverse the middle 6 m of a 10-m walkway (5 repetitions/assessment). Secondary outcomes include: 1. Gait endurance: The distance walked over 6 minutes. 2. Fall Frequency: Number of falls experienced weekly. 3. Leg Motor Fugl-Meyer (FM) Score: Assessed according to the FM rating system. 4. Dorsiflexion Active Range of Motion (AROM) and torque: The paretic foot will be placed in an articulated brace which maintains the ankle at neutral during idling, while fixing the tibia perpendicular to the ground and the femur horizontal to the ground. The brace will be instrumented with an electro-goniometer and torque meter to automatically measure the maximum dorsiflexion AROM and torque (over 3 trials). 5. EEG Map: Subjects will undergo 64-channel EEG recording as they engage in 100 alternating 10-s long epochs of idling and attempted dorsiflexion. The EEG ERD/ERS, defined as the drop/rise in alpha (8-12 Hz) and beta (13-30 Hz) band power during attempted dorsiflexion (compared to idling), will be calculated and averaged over all epochs and across all channels. A pre-intervention baseline for each outcome will first be established. Subsequently, measurements will be performed at 1 week intervals during the intervention phase (total of 3), immediately after the intervention phase, as well as 1 and 3 months after completion of interventions. The primary efficacy outcome and endpoint will be gait velocity immediately after the intervention phase. Aim 2 (subgroup analysis of Phase II clinical trial) Since stroke is a heterogeneous disease, responsiveness to rehabilitation therapy is not uniform across all subpopulations. Hence, it is important to ensure that any new therapy, e.g. BCI-FES therapy, is matched to subpopulations that will benefit the most. The following set of baseline characteristics will be assessed during the pre-intervention phase (Fig. 6, Phase 2) for Groups 1 and 2 to determine which features influence responsiveness to BCI-FES therapy: 1. Baseline gait velocity, dorsiflexion AROM and torque: Baseline gait velocity and dorsiflexion AROM and torque will be taken from Aim 1. 2. TA volitional electromyogram (EMG): TA EMG will be assessed by having subjects attempt dorsiflexion while seated with tibia perpendicular to ground. EMG will be acquired by a bioamplifier with surface electrodes placed over the TA muscle. Subjects will be categorized as either

having TA EMG or no response (no detectable EMG activity after 4 attempts).

3. EEG features: Movement induced EEG ERD/ERS and its spatial distribution in  $\mu$  (8-12 Hz) and  $\beta$  (13-30 Hz) bands may change after stroke. Since BCI-FES therapy depends upon and possibly alters  $\mu$  and  $\beta$  modulation, it is important to understand how the baseline ERD/ERS magnitude affects response to the therapy. EEG prior to the first BCI-FES session will be taken from Aim 1.

4. Nottingham Sensory Score: Baseline sensory impairment, as assessed by the Nottingham sensory system, can help determine if BCI-FES therapy can circumvent this requirement or not. Note that subjects will be informed that they are to refrain from starting any additional new physical therapies or other studies in stroke recovery for the entire duration of the study (including post-therapy visits). Subjects will be informed that those who become involved in outside therapy will be removed from the study as this may confound the scientific results.

Aim 3 (Mechanism study, not a clinical trial): In order to elucidate the plasticity mechanism underlying BCI-FES therapy, it is necessary to compare BCI-FES therapy to a control. Hence, two new groups of chronic stroke subjects with foot-drop will be recruited (10 subjects each, same selection criteria as in Aim 1). The first group (Group 3), will undergo BCI-FES therapy as in Aim 1 (no concurrent physiotherapy). The second group (Group 4), will undergo BCI-robotic orthosis therapy. This comparison will allow us to determine if the mechanism of BCI-FES therapy is via enhanced sensory feedback, or via co-incident activation of upper and lower motor neurons. BCI-robotic orthosis therapy is similar to BCI-FES therapy, except that the FES system is replaced by a robotic orthosis that dorsiflexes the foot when attempted dorsiflexion is detected from EEG. The use of a BCI-robotic allows us to test if sensory feedback is the primary driver of the neurological improvements or if co-incident firing between the brain motor cortex and muscles is the primary driver. It should be noted that BCI-FES and BCI-robot therapies both provide sensory feedback, but only BCI-FES provides co-incident firing between the brain motor cortex and the muscles. The primary outcome examined here will also be gait velocity. Other secondary outcomes include gait endurance and TA volitional EMG, as described above.

Assessments are done on the same schedule as in Aim 1. This device will be used because, unlike EMG, NIRS systems are optically based. This allows for continuous monitoring at the muscle while the FES system is in use. EMG systems do not allow for continuous measurements when using FES, given that EMG systems measure electrical activity at the muscle that cannot be separated from the electrical activity of the FES system. TR-NIRS data will

provide insight into the metabolic changes at the TA muscle that can be compared between patients in the BCI-FES and BCI-robotic orthosis groups. This data will not only aid the stroke research community but will also aid the rehabilitation field in understanding healing dynamics post injury. The coherence between the Cz EEG electrode and the TA EMG will be calculated, known as  $w$ . The correlation between gait velocity and  $w$  will be calculated across the entire duration of study for all subjects. This will be repeated for both BCI-FES groups and BCI-robotic orthosis groups. Comparing the correlation between these 2 groups can provide insight into which of the above mechanisms is primarily driving plasticity.

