**Progress Report**

## **UCI Progress**

**Please provide a detailed description of the progress of the study, including a brief summary of any interim findings or trends, and plans for the next approval period:**

Our phase 2 clinical trial has concluded recruitment, enrollment and treatment. The plan for the next approval period is to complete post treatment assessments and data analysis. Interim data was reviewed confidentially by the DSMB at their meeting in November 2023 and approved. The DSMB Meeting report was uploaded to the attachment section. Subject status breakdown: Aim 1: 168 assessed for eligibility; 106 were ineligible, 62 were randomized to study; 54 received intervention per protocol and completed all assessments, 1 withdrew from treatment but completed assessments, 4 withdrew consent from study, 2 were removed by physician; 1 is ongoing for final assessment; Aim 3: 23 assessed for eligibility; 13 were ineligible, 10 were randomized to study; 8 received intervention per protocol and completed all assessments, 0 withdrew from treatment but completed assessments, 0 withdrew consent from study, 0 were removed by physician; 2 are ongoing for final assessment. Aims 1 and 3 were the only 2 aims that were enrolling subjects and have closed enrollment. Clinicaltrials.gov has been updated to reflect close of enrollment.

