#### **Statistical Considerations**

Is a statistical analysis plan appropriate for this qualitative study design?

Yes

Describe the statistical methods for the stated specific aims and hypotheses. Your analysis plans should match the stated study specific aims and hypotheses:

Aim 1: The study design is a parallel randomized controlled trial with two arms: BCI-FES dorsiflexion therapy and dose-matched conventional physical therapy. A total of 80 subjects (which includes 10% attrition) will be randomized with 1:1 ratio into the two study arms. The primary outcome is gait velocity and the secondary outcomes are gait endurance, fall frequency, leg motor FM score, and dorsiflexion AROM and torque. Outcomes measures will be evaluated at baseline, weekly during therapy, immediately post-intervention, and 1- month and 3-months post-therapy. The primary efficacy analysis (with intent-to-treat analysis with respect to treatment randomized) will be based on a linear mixed model (LMM) with gait velocity measured at baseline weeks 1-4 (time 0, 1, 2, 3, and 4) with time, treatment group and group by time interaction assess the difference in the rates of change (improvement) in gait velocity between treatment groups. Model estimation will be based on restricted maximum likelihood (REML) with unstructured covariance among repeated measurements over time. The LMM will also be applied to evaluate group difference for secondary outcomes and secondary endpoints at 1- and 3-months post-therapy. In order to determine if  $\mu$  and  $\beta$  ERD/ERS significantly changes over the 4 weeks of therapy, the ERD and ERS magnitude will be calculated for each EEG channel across all attempted dorsiflexion epochs, and for each assessment. The Mann-Whitney U test will be used to determine if any significant changes in the magnitude of ERD/ERS at each assessment with respect to the baseline. Based on the findings, each subject will be categorized as demonstrating significant changes in ERD/ERS or not. Next, all subjects will also be categorized on whether they experienced a detectable increase in gait velocity (defined as an increase in gait velocity of  $>0.16$  m/s with respect to baseline). A Chi-square test will be used to assess if there is a difference between the proportion of those with changes in ERD/ERS magnitude in those who had gait improvement within the BCI- FES therapy group. This will also be repeated for the control group. In addition, to determine if the presence of significant ERD/ERS changes was affected by group, the Chi-square test will be repeated by using BCI-FES group as the observation and the control group as the expected values. Aim 2: Data from Aim 1 will be used for analysis in this aim. The primary outcome is gait velocity immediately post-BCI-FES therapy, and the secondary outcomes are the same as in Aim 1. To test whether specific stroke features (e.g. baseline gait velocity, dorsiflexion AROM, etc.) modify response to treatment over

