**Power Analysis:** For Aims 1 and 2, the power analysis was based on a LMM with two treatment groups and 5 repeated measures (baseline and after weeks 1-4) with a significance level of 0.05. Previous studies have examined the clinically meaningful gait improvement (minimal clinically important difference) of 0.16 m/s, including a multicenter randomized clinical trial that includes conventional physical therapy. Thus, to ensure clinically meaningful effect size, we assume conventional therapy will have an improvement of 0.25 m/s after 4 weeks of treatment. Data from prior studies as well as our own preliminary data (n=9) found that the between-subject variance in gait velocity of about 0.16 m/s and the within-subject correlation of about 0.95. Table 1 below shows the power to detect improvement of BCI-FES over conventional therapy of 30% - 40%. Thus, for the proposed study with n=80 patients (40 per arm) has 92% to 94% power to detect an effect size/improvement of 35% for various between-subject variance (0.15 m/s to 0.17 m/s) in determining treatment efficacy (Aim 1). We note that n=80 total has been intentionally inflated in order to accommodate the objectives of aim 2 to examine modifying factors, such as TA MEP (primary modifying factor), on treatment. That is, for n=30 per arm the power to determine efficacy (aim 1) is 85% for detecting an effect size/improvement of 35% (between-subject variance 0.16 m/s); thus, increasing to n=40 allows for detecting modifying factor on treatment (aim 2) when the interaction effect smaller (effect size 28% can be detected with 79% power). Table 1: Power to detect improvement in gait velocity due to BCI-FES over conventional therapy for n=80 with various between-subject variance (aim 1). Between-Subject Variance Effect Size (Improvement) 0.15 0.16 0.17 30% 87.3% 85.2 % 83.0% 35% 94.5% 93.5% 92.1% 40% 98.3% 97.7% 97.0% Aim 3: Total sample size of n=20 will have 82% power to detect an R-square of 0.16 (attributed to the effect of interest, e.g., w x group) adjusted for baseline measurement and main effects whose total contribution R-square is 0.5 (for 3 independent variables) in a multiple regression model.

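### Aim 1 names gait velocity at the end of the intervention as its primary endpoint but tests a difference in slopes over weeks 0-4, and the quoted 92-94% power fits only the slope

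*Combined protocol and SAP*

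**What the plan says.** - **Endpoint** (Study Design, endpoint definitions, Aim 1): "The primary efficacy outcome and endpoint will be gait velocity immediately after the intervention phase". This is a single visit.
- **Primary test** (Statistical Considerations, Aim 1): a linear mixed model on gait velocity at times 0, 1, 2, 3 and 4, fitted by REML with unstructured covariance, with "group by time interaction assess the difference in the rates of change (improvement) in gait velocity between treatment groups". No end-of-intervention contrast is named.
- **Power** (Statistical Considerations, Power Analysis): a mixed model with two groups and "5 repeated measures (baseline and after weeks 1-4) with a significance level of 0.05". Sidedness is not stated. At 40 per arm the study "has 92% to 94% power to detect an effect size/improvement of 35" per cent, over variances from 0.15 to 0.17. Two further figures are given: "for n=30 per arm the power to determine efficacy (aim 1) is 85" per cent, and "effect size 28% can be detected with 79% power". The second is tied to the Aim 2 interaction.
- **Later visits** (Statistical Considerations, Aim 1): "The LMM will also be applied to evaluate group difference for secondary outcomes and secondary endpoints at 1- and 3-months post-therapy". The model as written stops at time 4.

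**The concern.** The declared endpoint asks how far apart the arms are when treatment ends. The described test asks whether the arms improve at different rates over the whole treatment period. The answers coincide when the arm difference grows in a straight line from baseline to week 4. If the benefit comes early and then levels off, or appears only late, the slope estimate and its p-value can differ from the end-of-intervention difference. The power statement is also read as support for the declared endpoint, although it may belong to the other quantity. With two candidate primary analyses in the text, the report could not show which one was prespecified.

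**Working it through.** **Inputs from the Power Analysis.** Conventional therapy gains 0.25 m/s over 4 weeks, so a 35% advantage is 0.35 × 0.25 = 0.0875 m/s at week 4. Variance v = 0.16, within-subject correlation ρ = 0.95, n = 40 per arm, level 0.05. The plan attaches m/s to the 0.16 but calls it a variance. Read as a standard deviation it gives about 100% power for the slope and does not reproduce Table 1.

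**Assumptions added here.** Two-sided test, normal approximation, compound symmetry (the plan gives only one correlation for power).

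**Standard errors.** The times 0-4 have sum of squares 10 about their mean.

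- Slope × 4: 4·√[v(1−ρ)/10 · 2/n] = 4·√(0.16·0.05/10 · 2/40) = 0.0253
- Week-4 change from baseline: √[2v(1−ρ) · 2/n] = √(0.016 · 2/40) = 0.0283
- Week-4 value adjusted for baseline: √[v(1−ρ²) · 2/n] = √(0.0156 · 2/40) = 0.0279

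**Power = Φ(effect/SE − 1.96).**

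| Test, two-sided, 35% effect, v = 0.16 | Effect/SE | Power |
|---|---|---|
| Slope | 3.459 | 93.3% (stated 93.5%) |
| Change from baseline | 3.094 | 87.2% |
| Baseline-adjusted | 3.133 | 88.0% |

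**Other stated figures.** Over the nine cells of Table 1 the slope test is within 1.0 point. The week-4 contrasts fall 2.4 to 10.0 points short. At 30 per arm (stated 85%) the slope gives 85.0% and the contrasts 76.4% and 77.4%. For the 28% effect (stated 79%), computed as a plain two-arm comparison, the slope gives 79.0% and the contrasts 69.7% and 70.8%.

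**What the slope recovers when the gain is not linear.** Under compound symmetry the slope weights are (−2, −1, 0, 1, 2)/10. Let D be the week-4 arm difference.

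- Difference complete by week 1: slope = D(−1 + 0 + 1 + 2)/10 = 0.2D, and × 4 = 0.8D.
- Difference only at week 4: slope = 2D/10 = 0.2D, and × 4 = 0.8D.

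At 0.8 × 0.0875 = 0.070 m/s the slope test has 79.0% power at 40 per arm, while the contrasts keep 87-88%. Both profiles are illustrative; the plan gives no expected trajectory.

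**Dependence on the covariance.** The analysis model is unstructured, so compound symmetry need not hold in the data. In each case below the variance of the change score stays at 0.016, so the change contrast keeps 87.2%.

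- *Serially decaying correlation*, 0.95 between baseline and week 4: the generalised least squares slope × 4 has SE 0.0283 and 87.2% power, and it recovers about 100% of D in both profiles.
- *Random slopes* making up half of the change-score variance: residual variance 0.004 and slope variance 0.0005. The variance of slope × 4 is 16·(0.004/10 + 0.0005) = 0.0144, SE = √(0.0144 · 2/40) = 0.0268, power 90.3%, a gap of about 3 points.

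The penalty for testing the declared endpoint therefore runs from about 0 points (serial decay) to about 6 (compound symmetry, 93.3 − 87.2).

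**The case against.** The strongest reply is that test and power already agree. Numeric times 0 to 4, the reference to rates of change, and the Aim 2 text, which tests whether the slope of an interaction is zero, make linear time the plain reading. The Power Analysis describes the same five-visit model and expresses the effect as improvement over 4 weeks, which is four times the slope under linearity. On that view only the endpoint sentence is out of step. This largely stands: the two-sided slope test does reproduce the power figures. What remains is that the sentence out of step is the one that defines the primary endpoint, and that linearity and sidedness are left to inference.

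A second reply is that the loss is modest, since the declared endpoint still has 87-88% power at the planned size. That also stands. A reader might go further and conclude that the trial is underpowered, because the progress report says "62 were randomized to study" for Aim 1. At 31 per arm (even split assumed) the same formulas give 86.1% for the slope and 77.7-78.8% for the contrasts. Most of the distance from the stated figure is then the shortfall in enrolment, which is a separate matter.

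A reader might also infer a one-sided test, because one-sided 5% week-4 contrasts fit the nine Table 1 cells within 1.0 point. Nothing in the documents says one-sided, and five repeated measures point to the slope.

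**Conclusion.** The declared primary endpoint and the described primary test are different quantities unless the arm difference grows linearly. On the natural two-sided reading the quoted 92-94% power belongs to the slope. The declared endpoint has 87-88% under compound symmetry, a penalty of 5 to 6 points; across plausible covariances it is about 0 to 6 points at 40 per arm. The estimates can diverge by as much as 20% of the effect in the two profiles tried under compound symmetry, and hardly at all under serially decaying correlation. These figures rest on the plan's variance and correlation, the normal approximation, and covariance shapes that the plan does not give.

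The documents do not show that the stated power is wrong for the test described, or that the slope must misstate the end-of-treatment effect. Nor do they support an inference that the choice of analysis was informed by results: the interim review is described as confidential and the investigative team as blinded. This is an inconsistency that should be corrected before analysis. It does not invalidate the design.

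**What to change.** In a dated amendment, before by-arm data are analysed, make the endpoint definition, the primary analysis and the power statement name one estimand, and state that the test is two-sided. There are two ways to do this:

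- **(a) Keep the endpoint.** Name the end-of-intervention arm difference as the primary contrast, baseline-adjusted or with a common baseline mean, from the mixed model with time as categorical. Restate power as about 87-88% at 40 per arm under the compound-symmetry assumption.
- **(b) Keep the test.** Redefine the primary endpoint as the arm difference in rate of change over weeks 0-4, state linear time, and keep the stated power.

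In either case report both the slope and the end-of-intervention contrast. As a secondary correction, extend the written model to include the 1- and 3-month visits that it is said to analyse.

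The cost is wording and one extra analysis, with no new data. Option (a) means quoting a lower power and changing the primary test after treatment has ended. Option (b) ties the primary claim to linearity.

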#### Exclusion Criteria

Exclusion Criteria: 1. A major, active, coexistent medical, neurological (apart from stroke) or psychiatric disease (apart from stroke), including alcoholism or dementia, orthopedic injuries, that substantially affects gait. \*\*Because old orthopedic injuries may or may not affect gait, at the discretion of the site's study PI, exclusion criterion #2 related to orthopedic injuries can be waived if the joint/muscles are back to normal motor and range of motion function. 2. A major medical disorder that substantially reduces the likelihood that a subject will be able to comply with all study procedures or safely complete study procedures. This includes, but not limited to documented serious cardiac conditions, serious pulmonary conditions, legal blindness, end stage renal or liver disease, pulmonary embolism or deep venous thrombosis. 3. Resting systolic blood pressure above 170, diastolic blood pressure above 100 at screening and baseline evaluations 4. Implanted electronic device (e.g. pacemaker) or skull metallic implants (e.g. cranioplasty plate covering the leg motor area) with which study research procedures are contraindicated or incompatible. 5. Deficits in communication that interfere with reasonable study participation: language or attention impairment (score>1 on NIH Stroke Scale items 9 and 11, respectively) 6. Significant cognitive impairment, defined as Montreal Cognitive Assessment score < 22 (For those with aphasia: \*\*Because Montreal Cognitive Assessment scores may be difficult to interpret for patients with aphasia, at the discretion of the site's study PI, exclusion criterion #5 ("MoCA score cannot be <22") can be waived) 7. A new symptomatic stroke occurs apart from the index stroke during the screening process and prior to randomization 8. Life expectancy < 6 months 9. Skin breakdown over electrical stimulation sites; 10. Received chemical denervation (eg Botox) to legs in the preceding 6 months, or expectation that chemical denervation will be administered to the leg prior to expected completion of the study 11. Unable or unwilling to perform study procedures/therapy, or expectation of non-compliance with study procedures/therapy 12. Pregnancy; 13. Significant pain (visual analog scale >4), chest pain, or shortness of breath with walking. 14. Receiving any outside concurrent physical therapy involving the lower extremities after enrollment in the study up to 1 month post treatment 15. Any general medical condition and psychosocial situation that substantially interferes with reasonable participate in study appointments 16. Non-English

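### Removing randomised subjects who take outside therapy conflicts with intent-to-treat and can bias the 1- and 3-month comparisons

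*Combined protocol and SAP*

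**What the plan says.** The endpoint definitions under Study Design (note at the end of the Aim 2 list) tell subjects not to start other physical therapy or stroke-recovery studies "for the entire duration of the study (including post-therapy visits". They add that "those who become involved in outside therapy will be removed from the study as this may confound the scientific results".

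Statistical Considerations, Aim 1, states: "The primary efficacy analysis (with intent-to-treat analysis with respect to treatment randomized) will be based on a linear mixed model (LMM"), fitted to gait velocity at weeks 0 to 4 by REML with unstructured covariance. The same model is to be used for "secondary endpoints at 1- and 3-months post-therapy". The Aim 1 hypothesis (Background & Purpose) is that gains are both greater and longer-lasting than with conventional therapy.

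The documents do not say whether removed subjects are still assessed, how their missing visits are handled, or which effect is targeted when outside therapy is taken. They plan no sensitivity analysis. They also do not say that data collected before removal are discarded.

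The length of the ban is inconsistent. Exclusion criterion 14 reads "Receiving any outside concurrent physical therapy involving the lower extremities after enrollment in the study up to 1 month post treatment", whereas both places in Study Design that mention the ban extend it over the whole study.

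**The concern.** Starting outside therapy happens after randomisation and may reflect how well the assigned therapy worked: a subject who gains little, or who slips back after week 4, has more reason to look elsewhere. If such subjects are removed, their later visits are missing by rule. If that happens more often in one arm, the subjects still assessed at 1 and 3 months are no longer the groups that were randomised.

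The stated reason is to avoid confounding. Outside therapy does change what a late comparison measures, but removing the subject exchanges that problem for selection on a post-randomisation event. At stake is the evidence on durability, which rests on two visits after treatment. More removal of declining controls would understate a real benefit; more removal of declining BCI-FES subjects would overstate it.

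**Working it through.** **Inputs from Statistical Considerations.** Between-subject variance 0.16; within-subject correlation 0.95; five measurements (weeks 0 to 4); 40 per arm; "with a significance level of 0.05" (taken as two-sided); and "we assume conventional therapy will have an improvement of 0.25 m/s after 4 weeks of treatment". A 35% advantage is therefore 0.25 × 0.35 = 0.0875 m/s.

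**Reproducing the plan's figure.**
- Slope difference per week: 0.0875/4 = 0.0219.
- SD of a subject's slope under compound symmetry: √(0.16 × 0.05/10) = 0.0283, where 10 is the sum of squares of the times 0 to 4.
- Power with 40 per arm: 93.3%, against 93.5% in Table 1.

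All nine cells of Table 1 agree within one percentage point, so this variance model is the plan's own and can be used below.

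**Worst-case bias at a late visit.** Assume that removal occurs after week 4, in one arm only, and takes exactly the subjects whose later value falls furthest below what their five earlier visits predict.
- Residual variance: 0.16 × 0.05 = 0.008.
- SD of a later value given five earlier visits: √(0.008 × (1 + 0.95/4.8)) = 0.0979 m/s, where 4.8 = 0.05 + 5 × 0.95.
- If a fraction p is removed, the mixed-model mean for that arm shifts by 0.0979 × φ(z)/(1 − p), with z the upper-p normal quantile.

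| Removed from one arm | p | φ(z)/(1 − p) | Shift (m/s) | Share of 0.0875 |
|---|---|---|---|---|
| 1 of 31 | 3.2% | 0.0747 | 0.007 | 8% |
| 2 of 31 | 6.5% | 0.1348 | 0.013 | 15% |
| assumed 10% | 10% | 0.195 | 0.019 | 22% |

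The figure of 31 per arm is an assumption: the Progress Report gives 62 randomised in Aim 1 but no split. The benchmark 0.0875 m/s is the powered 4-week difference; the plan states no target effect at 1 or 3 months.

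**Milder and neutral cases.** Suppose removed subjects would have been d m/s worse than the model predicts, with the same d in both arms. The bias is then the difference in removal rates times d. For 10% against 5% and d from 0.05 to 0.16 m/s, it is 0.0025 to 0.008 m/s (3% to 9% of 0.0875). With equal rates it is zero.

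**Simulation.** Settings: 40 per arm, the plan's variance and correlation, a true difference of 0.0875 m/s held to 3 months, removal after week 4, and all pre-removal data in the model. The removal rates are assumptions.

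| Removal driven by | Control vs BCI-FES removed | Estimate, full follow-up (m/s) | Estimate, with removal (m/s) |
|---|---|---|---|
| observed week-4 change | 20% vs 5% | 0.088 | 0.088 |
| unobserved later decline | 10% vs 5% | 0.087 | 0.080 |
| unobserved later decline | 15% vs 5% | 0.088 | 0.075 |
| unobserved later decline | 20% vs 5% | 0.087 | 0.069 |
| unobserved later decline | 20% vs 20% | 0.087 | 0.087 |

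Bias therefore needs two things together: removal that depends on values not yet observed, and a difference between arms.

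**The case against.** A reader might infer that the rule breaks the intent-to-treat primary analysis. The documents do not support that. The intent-to-treat label is attached to the week 0-4 model, nothing says earlier data are dropped or that a subject leaves the randomised arm, and a REML mixed model uses all visits before removal. It is valid if removal depends only on values already observed. The removal sentence also describes what subjects are told; it is not an exclusion from the analysis population, and Statistical Considerations contains none. These points stand, and they confine the main exposure to the secondary 1- and 3-month comparisons.

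A reader might also infer that material bias has occurred. The Progress Report lists 2 of 62 Aim 1 subjects as removed by a physician, for any reason, and 4 who withdrew consent. The only removal reason given, under Early Termination(s), is intolerance of treatment. So a 10% removal rate for outside therapy is not indicated. Zero cannot be confirmed either: one reason is given against two removals, and a case could lie among the withdrawals of consent.

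Setting values after outside therapy to missing can be a legitimate choice if the target is the effect without such therapy. That also stands, but the plan neither names that target nor tests the missing-data assumption it needs.

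Finally, treatment is over and one Aim 1 subject awaits final assessment, so retaining subjects can change little now. The analysis and reporting can still be changed.

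**Conclusion.** The conflict is real and no text resolves it: intent-to-treat is promised, while a post-randomisation event that may be related to outcome ends participation with no provision for continued assessment. That removal means the end of assessment is an inference, but a reasonable one: the Progress Report counts a subject who stopped treatment and completed assessments separately from those removed. That entry also shows that follow-up after stopping treatment is feasible here.

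The consequence is possible bias at 1 and 3 months, not a demonstrated failure of the primary analysis. Its size is unknown. On the plan's variance and correlation, the worst case is 0.007 to 0.013 m/s for 1 or 2 removals in an arm of 31 and 0.019 m/s at 10%; it falls to zero when removal and shortfall match across arms. The change is worth making because it is cheap and protects the durability claim. If exclusion criterion 14 sets the length of the ban, removal would not be triggered between 1 and 3 months, so the exposure also depends on how that inconsistency is resolved.

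**What to change.** 1. State that taking outside therapy neither ends assessments nor excludes a subject from analysis. Keep every randomised subject on the assessment schedule, including any still awaiting visits, and analyse all available data by randomised arm.
2. Record the start date and type of any outside therapy. Report outside therapy and removals by arm, with reasons.
3. Add sensitivity analyses at 1 and 3 months: one that sets values after the start of outside therapy to missing, and one that allows missingness to depend on unobserved values.
4. Reconcile the length of the ban between exclusion criterion 14 and Study Design. Whether outside therapy is permitted, and for how long, is for the study team.

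The cost is some wording in the protocol and consent text, a small addition to data collection, and two extra analyses. The downside is small: some later values will reflect study therapy plus outside therapy, which the first sensitivity analysis addresses.
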